The circadian system is controlled by a central master clock and is a key determinant of sleep timing. The master clock is synchronized with the 24-hour day by external cues via a process called entrainment. Light is the most influential external entrainment cue. Under normal entrainment, the circadian system promotes arousal during the day and allows sleep during the night. Sleep quality and length are optimal when they occur during an individual's "biologic" or "circadian" night. Circadian abnormalities contribute to inappropriate sleep timing, impaired sleep quality and decreased sleep quantity. These three elements of sleep disruption have been clearly shown in critically ill patients,¹⁵⁻¹⁷ and together with circadian abnormalities these elements form a vicious cycle. Circadian abnormalities are defined in this proposal as misalignment and decreased amplitude. We assert that optimal sleep promotion and therefore optimal treatment and prevention of delirium requires the promotion of normal circadian entrainment. The proposed project supports this by investigating the influence of ICU day-night light patterns on circadian abnormalities, examining the association between circadian abnormalities and duration of delirium and piloting a daytime bright light intervention (Figure 1).

Premise for Aims 1 and 2: ICU day-night light patterns conflict with circadian entrainment and cause circadian abnormalities. External cues for entrainment include light, meal schedule, and physical activity. As noted above, light has by far the greatest biologic influence on entrainment.¹⁸ The robustness of entrainment and vulnerability to disruption are determined by the timing, intensity (lux), and duration of a light dose.¹⁹ Normal entrainment requires bright light exposure during the day (wake) period and dim or no light during the night (sleep) period. Daytime bright light interventions deliver at least 1,000 lux and more typically deliver 2,500 to 10,000 lux over 30 minutes to several hours.^{20, 21} During the night, short bursts of bright light (e.g., 5 minutes) at relatively lower intensities (e.g., 100 or 250 lux) can cause circadian abnormalities.¹⁹ Interventions aimed at ICU sleep promotion have focused on lowering overnight

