Aim 2 Analytic Approach: Circadian measures will be analyzed as in Aim 1. Sleep disruption will include two measures: (1) total amount of sleep, a continuous variable calculated as the number of sleep epochs in a 24 hour period and (2) overnight sleep efficiency, a continuous variable calculated as the percent of epochs scored as sleep between 22:00 and 06:00. Sleep will be based on standard Philips Actiwatch Software algorithms. Days of Delirium will be calculated as the sum of days on which the patient is delirious. Delirium will be considered present if either the CAM-ICU or the chart abstraction is positive for a given calendar day. Patients will be censored at day 30 or at hospital discharge.^{59, 60} Confounder and effect mediator variables: Severity of illness, age, and gender will be treated as in Aim 1. Ventilator use will include invasive and noninvasive positive pressure ventilation and will be quantified as ventilator-free days based on published algorithms.⁶¹ For sedative-hypnotic medications, equivalent daily doses of benzodiazepines and narcotics will be calculated using published algorithms.^{62, 63} Propofol and dexmedetomidine total daily dose will be recorded and included in the models.

Testing for Associations: Multivariable Poisson models will assess the associations between circadian misalignment and amplitude and days of delirium. Models will be adjusted for age, severity of illness, ventilator-free days, dose of sedative medication, and measures of sleep disruption. We will test for modification of the associations between misalignment and amplitude and days of delirium by age, sedative-hypnotic medication dose and measures of sleep disruption. Linearity, serial correlation, and model fit will be addressed as in Aim 1. **Power Calculation:** Patients with delirium on the day of enrollment will be excluded, our effective sample size will be reduced by 20% to 80 participants. Assuming two-sided alpha of 0.05, 90% power, overdispersion of 20%, and a mean of 3 days of delirium,⁴ our sample of 80 allows the detection of a minimal risk ratio of 1.12 for each 60 minutes of misalignment. Under the same assumptions, our sample of 80 will detect a minimal risk ratio of 1.08 for each change of 100ng of aMT6s.⁶⁴

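### The Aim 2 power statement gives no exposure SD and no allowance for about nine covariates; with the Aim 1 SDs, risk ratios of 1.12 and 1.08 are not detectable at 90% power

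*Combined protocol and SAP*

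**What the plan says.** All of this is in Statistical Considerations of the combined protocol and SAP.

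- **Analysis (Aim 2, Testing for Associations).** Days of delirium are regressed on misalignment and amplitude in multivariable Poisson models: "Models will be adjusted for age, severity of illness, ventilator-free days, dose of sedative medication, and measures of sleep disruption". The text just before it defines two sleep measures and benzodiazepine and narcotic equivalents, and adds: "Propofol and dexmedetomidine total daily dose will be recorded and included in the models".
- **Power (Aim 2, Power Calculation).** Patients delirious at enrollment are excluded, so "our effective sample size will be reduced by 20% to 80 participants". The inputs are introduced with "Assuming two-sided alpha of 0.05, 90% power, overdispersion of 20%, and a mean of 3 days of delirium". The results are that "our sample of 80 allows the detection of a minimal risk ratio of 1.12 for each 60 minutes of misalignment", and a ratio of 1.08 per 100 ng of aMT6s.
- **Exposure SDs.** The Aim 2 text gives none. The only ones in the document are in the Aim 1 power text: 95 minutes for misalignment and 180 ng for amplitude.

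**The concern.** The adjustment set comes to nine terms: age, severity, ventilator-free days, four sedative doses (benzodiazepine equivalents, narcotic equivalents, propofol, dexmedetomidine) and two sleep measures. Gender, named as a confounder but absent from the adjustment sentence, would make ten. Interaction tests come on top.

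In an adjusted model the variance of the exposure coefficient is multiplied by 1/(1 − R²), where R² is the share of the exposure's variance explained by the covariates. No such quantity is among the power inputs. The plan itself gives reason to doubt that it is zero. The Background says of the elements of sleep disruption that "together with circadian abnormalities these elements form a vicious cycle", and the Aim 2 rationale treats the sleep measures as possible confounders.

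Aim 2 is meant to support later work on entrainment as a delirium treatment. If 90% power is credited to the adjusted model and that model has much less, a null result would carry less information than the plan implies.

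**Working it through.** **Inputs.** From the Aim 2 power text: two-sided alpha 0.05, 90% power, mean 3 days, n = 80, and 20% overdispersion, read as variance = 1.2 × mean. From the Aim 1 power text, assumed to carry over: SD 95 min = 1.583 units of 60 min, and SD 180 ng = 1.80 units of 100 ng. Population rho-squared is not in the documents; the range 0 to 0.3 is an assumption.

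**Formula.** For one roughly normal exposure in a Poisson model with dispersion φ:

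ln(RR) = (1.960 + 1.282) × √(φ / (n × mean × (1 − R²))) / SD

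**Step 1: the plan's own figures, no covariates (R² = 0).** √(1.2/240) = 0.0707, and 3.242 × 0.0707 = 0.2292.

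- Misalignment: exp(0.2292/1.583) = 1.156, against the printed 1.12.
- Amplitude: exp(0.2292/1.80) = 1.136, against the printed 1.08.

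Power at the printed values is Φ(ln(RR) × SD / 0.0707 − 1.960):

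- 1.12: Φ(2.538 − 1.960) = 72%.
- 1.08: Φ(1.959 − 1.960) = 50%.

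Simulation with quasi-Poisson fits gave 72% and 48%. By the formula, 90% power at the printed values would take about 131 and 220 patients.

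The printed pair was not reproduced. One- and two-sided tests, 80% and 90% power, dispersion from 0.8 to 1.44, n of 80 or 100, and alternative variance forms were tried. Some settings approach 1.12 alone (80% power with no overdispersion gives 1.121, but then 1.106 for amplitude); none gives both. The reason is structural: ln(1.12)/ln(1.08) = 1.47 (1.33 to 1.63 allowing for rounding), while the Aim 1 SDs give 1.80/1.583 = 1.14.

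**Step 2: nine covariates.** Even unrelated covariates have an expected sample R² of 9/79 = 0.114. With population rho-squared ρ², the effective R² is 1 − (1 − ρ²) × 70/79.

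| ρ² (assumed) | Effective R² | φ | RR at 90% power, per 60 min / per 100 ng | Power at 1.12 / 1.08 |
|---|---|---|---|---|
| 0 | 0.114 | 1.2 | 1.166 / 1.145 | 67% / 45% |
| 0.1 | 0.203 | 1.2 | 1.176 / 1.153 | 62% / 42% |
| 0.2 | 0.291 | 1.2 | 1.188 / 1.163 | 57% / 38% |
| 0.3 | 0.380 | 1.2 | 1.202 / 1.175 | 52% / 34% |
| 0 | 0.114 | 1.0 | 1.151 / 1.131 | 74% / 52% |
| 0.3 | 0.380 | 1.0 | 1.183 / 1.159 | 59% / 39% |

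Simulation with nine covariates gave 64% / 46% when they were uncorrelated with the exposure and 57% / 37% at ρ² = 0.2, within about three points of the φ = 1.2 rows.

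**Step 3: when adjustment costs nothing.** Covariates that predict delirium can lower residual dispersion, at best from 1.2 to 1.0. That offsets the variance inflation as long as the effective R² stays below 1 − 1.0/1.2 = 1/6, that is, ρ² below 1 − (5/6)(79/70) = 0.06.

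**The case against.** Three points on the other side have force.

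**The SDs are borrowed.** The Aim 2 text does not say that 95 minutes and 180 ng were used, and their failure to reproduce either figure suggests other inputs. A calculation without covariates returns 1.12 and 1.08 with SDs of about 121 minutes and 298 ng; SDs of about 136 minutes and 333 ng return them with an allowance of R² = 0.2. None of these values is in the document, and the methods paper cited for the calculation cannot be consulted here. A reader might infer that the printed ratios are too small to contain any covariate allowance. That follows only if the Aim 1 SDs apply. What can be shown is that no allowance is stated.

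**The 90% is not shown to be right for any analysis.** A reader might infer that it is correct for a one-covariate model and is lost only on adjustment. Step 1 does not support this: with the only SDs available, the unadjusted analysis already falls short. The gap from 1.12 to 1.156 comes before any covariate enters.

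**Adjustment need not cost power.** The number of covariates alone does not settle the loss, and age, severity and ventilator-free days are included because they should predict delirium. At full absorption of the overdispersion and ρ² near 0 there is no net loss (1.151 against 1.156). The passage tying sleep to circadian abnormality covers two of the nine terms and gives no size. The Background also places sleep disruption on the causal pathway, so adjusting for it changes the effect being estimated, which a variance-inflation factor does not capture.

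These points limit the claim about the size of the adjustment loss. They do not remove the mismatch between the model planned and the inputs listed.

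**Conclusion.** The point holds in this form. The Aim 2 power statement omits the exposure SDs and states no allowance for the roughly nine covariates in the model it is meant to support. Conditional on the Aim 1 SDs, 1.12 and 1.08 have about 72% and 50% power unadjusted. Adjusted, the range is about 67% to 52% and 45% to 34% with dispersion at 1.2. In the most favourable case examined (dispersion 1.0, ρ² = 0) it is about 74% and 52%, still well short of 90%.

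The conclusion rests on three assumptions: the Aim 1 SDs describe the 80 Aim 2 patients, 20% overdispersion means a variance factor of 1.2, and ρ² lies between 0 and 0.3. The shortfall at the printed ratios depends on the first two. The further loss from adjustment depends mainly on the third and on how much overdispersion the covariates absorb, so it can be given only as a range.

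**What to change.** Rewrite the Aim 2 power sentence so that it:

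1. states the SDs of misalignment and amplitude used, and their source;
2. restates both detectable risk ratios, or the power at 1.12 and 1.08, for the adjusted model over ρ² of 0 to 0.3 (plus the finite-sample part for the number of terms retained) and residual dispersion of 1.0 to 1.2, with both ranges labelled as assumptions;
3. says that, with the Aim 1 SDs, 1.12 and 1.08 are not detectable at 90% power. If other SDs were used, giving them would let the figures be checked.

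If the covariate list is shortened, 9/79 changes with it. The cost is one rewritten passage and less favourable stated figures. No extra patients or design change are needed, because the repair restates what 80 patients can detect.

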Aim 1 Analytical Approach: Individual sleep midpoint will be calculated as halfway between habitual bedtime and habitual waketime as indicated during patient/surrogate interview questionnaire. Light dose will be calculated as the sum of mean lux per hour for each hour between 08:00 and 17:00 (day dose) and 22:00 and 06:00 (overnight dose). A day/night dose ratio will then be calculated by dividing the daytime light dose by the overnight light dose. Light dose ratio will be treated as continuous exposure variables, with higher numbers indicating a more favorable (circadian) exposure and lower numbers indicating a less favorable (non-circadian) exposure. Circadian alignment and amplitude will be calculated using time series analysis of urinary aMT6s using smoothing techniques to examine characteristics of circadian rhythm: acrophase (maxima) and nadir (minima). Statistical measures will evaluate for serial correlation, seasonality (periodicity), and trend. Longitudinal cosinor techniques will be used to test for alignment of nadir and acrophase with normal circadian phase and amplitude (e.g., individual sleep midpoint and estimated normal peak aMT6s).⁵⁵ The degree of misalignment versus normal will be recorded in minutes. The amplitude of the cycle will be defined as one-half of the difference between the acrophase and nadir and will be recorded in nanograms (ng) per hour.³⁰ Normal values have been identified for aMT6s.^{30,56} The assessment of circadian abnormalities for association with light patterns will be solely based on aMT6s analysis. Heart rate, iButton gradient readings, and actigraphy activity counts will be evaluated via cosinor techniques analogous to the aMT6s analysis described above. Actigraphy activity counts will also be evaluated by visual inspection of normalized mean activity per hour (Fig 3) and as described by Duclos et al.³² Confounder and effect modifier variables: Severity of illness will be calculated according to the APACHE II algorithm⁵⁷ and expressed as a continuous variable. Sepsis will be expressed as a categorical variable (absent, septic, septic shock) based on the sepsis-3 criteria.⁴⁷ The risk of OSA will be expressed as a categorical variable (low risk, high risk) based on the STOP-BANG algorithm.^{46,58} Overnight ICU care events per the timestamp data described above will be calculated as the number of ICU care events per hour between 22:00 and 06:00. Average daytime and overnight room temperature will be calculated as a continuous variable.

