
Testing for Associations: Because both measures of circadian abnormality (misalignment and decreased amplitude) are continuous and normally distributed, multivariable linear regression models will test for associations, with light dose ratio serving as the exposure. Linearity of the associations will be examined graphically, and higher order terms will be considered as necessary. Models will be adjusted for age, gender, severity of illness, sepsis, risk of OSA, ICU care events per hour, and room temperature variables. We will test for modification of the association between light dose ratio and the outcomes by sepsis and risk of OSA. Because of the non-trivial intra-correlation coefficient expected from the serial correlation of the repeated outcome measures over time, models will employ generalized estimating equations with an auto-regressive correlation structure. Model fit will be evaluated with residual analysis, and significance will be defined as a two-sided p-value ≤ 0.05 . Power Calculations. For both continuous, normally distributed outcomes, power calculations assume a two-sided alpha of 0.05, power of 90%, a sample size of 100, and prevalence of covariates ranging from 20% to 50%. For minutes of misalignment, we further assume a mean of 180 minutes with a standard deviation of 95 and for amplitude a mean of 450 ng with standard deviation of 180.³⁰ Under these assumptions, our sample of 100 is sufficient to detect a range of minimal average shifts between 52-65 minutes of misalignment, and 98-123 ng of urinary aMT6 per

incremental change in the explanatory variables.

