Aim 3 Analytical Approach: Feasibility: Based on qualitative analysis, we will judge the intervention as feasible if it achieves at least 70% in each of the feasibility metrics: acceptance, tolerance, fidelity, and sustainability. Effect Size: Circadian abnormalities will be assessed as described under Aim 1. Using multivariable logistic regression, we will test for associations between bright light exposure and decreases in circadian misalignment and increases in circadian amplitude. The estimated association will inform the effect size in the design of future interventional studies.

SUBJECT POPULATION

Patients admitted to the Medical ICU and who meet inclusion / exclusion criteria will be recruited into this study. Decisionally impaired persons, females of childbearing potential and pregnant women who are admitted to the MICU and who meet inclusion / exclusion criteria might be recruited into this study; however, they will not be specifically recruited and subjects will be ≥ 50 years old and severe chronic brain injury is an exclusion criteria.

Table 2 (repeated)

Inclusion Criteria	Exclusion Criteria

- Hospital admission less than 30 hours as of noon on day of enrollment- Expected to stay in the MICU ≥ 24 hours after enrollment- Expected to produce ≥ 250 mL urine / day- Age ≥ 50 years- Able to understand English.	
At significant risk for pre-existing circadian abnormalities:
 
- Severe chronic brain injury (Injury greater than 30 days ago resulting in the inability to live independently) OR Acute brain injury of any severity (Injury less than 30 days ago including acute intracranial bleed, traumatic brain injury, central nervous system infection, tumor, hepatic encephalopathy)- Documented circadian disorder (<1% population) or blind/disease of the optic nerve- Current history of substance abuse including alcohol (use in last 30 days)- Transferred from an outside hospital- Homeless 
Unable to participate in study activities:
 
- History of bipolar disease (Bright light therapy possibly unsafe in this population).- Paralyzed (due to injury, disease or medications)

RECRUITMENT PROCEDURES

Patients will be screened daily from an automated list generated from the YNHH EMR. Patients who opt out of research participation via MyChart (patient information portal) will be excluded from this list.

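### Aim 3 names logistic regression for two outcomes that the plan defines as continuous, with no yes/no split or reference value stated

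*Combined protocol and SAP*

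**What the plan says.** All of this is in the combined protocol and SAP.

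- **Aim 3 Analytical Approach, Effect Size.** The outcomes are inherited: "Circadian abnormalities will be assessed as described under Aim 1". The model follows: "Using multivariable logistic regression, we will test for associations between bright light exposure and decreases in circadian misalignment and increases in circadian amplitude". Its purpose comes last: "The estimated association will inform the effect size in the design of future interventional studies". The paragraph gives no covariates, no arm coding, and no indication whether a patient contributes one value or several.
- **Aim 1 Analytical Approach.** For misalignment, "The degree of misalignment versus normal will be recorded in minutes". Amplitude "will be recorded in nanograms (ng) per hour".
- **Aim 1, Testing for Associations.** The model choice is tied to the type of outcome: "both measures of circadian abnormality (misalignment and decreased amplitude) are continuous and normally distributed, multivariable linear regression models will test for associations". Generalized estimating equations with an autoregressive structure are added because of the "non-trivial intra-correlation coefficient expected from the serial correlation of the repeated outcome measures over time". The adjustment set is listed: "Models will be adjusted for age, gender, severity of illness, sepsis, risk of OSA, ICU care events per hour, and room temperature variables".
- **Aim 3, Research Design.** Three arms of 5 patients: usual care, 4 hours of light daily and 8 hours of light daily. Light starts on study day 2.

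**The concern.** Logistic regression needs a categorical outcome, and the plan supplies two measured quantities. The reason that Aim 1 gives for a linear model applies equally to the same outcomes in Aim 3, and no reason is given for departing from it.

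To run the analysis as named, someone must decide what counts as a decrease in misalignment or an increase in amplitude, by how much, and relative to what. The plan leaves all of that open, so the choice could be made with the results in view. The product would be an odds ratio on that split. Anyone sizing a later trial on misalignment or amplitude would want the mean difference and SD, which the named model does not report. The Aim 3 Rationale gives calculating an effect size as a purpose of the pilot, so this affects half of the aim (Hypothesis 3.2). The other half, feasibility, is judged on percentages and is untouched.

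**Working it through.** The plan gives no power, effect size or cut-point for Aim 3, so there is no figure to reproduce. The check has three parts.

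**1. Is a split or reference value defined anywhere?**

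- The Aim 1 Analytical Approach says that normal aMT6s values exist, but gives no threshold.
- The Aim 1 Rationale treats absent rhythm as a 100% fall in amplitude. That is the extreme of a continuous scale and is not named as an Aim 3 event.
- Misalignment is measured against each patient's own sleep midpoint. That defines the measure, not a change in it.
- The schedule does contain a possible baseline. Enrolment is before 12:00 on day 1, urine is collected for 72 hours from enrolment or until MICU discharge, and light starts at 09:00 on day 2. The night of day 1 to day 2 therefore precedes the light, and at most two later nights (days 2–3 and 3–4) fall inside the urine window. The plan does not name the first night as the reference.

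So a split is absent, and a reference value is available but not designated.

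**2. What would depend on the split?** This is an illustration. Inputs: the Aim 1 planning mean of 180 min and SD of 95 min, normality, an assumed 60-min benefit, and assumed cuts at 60, 120, 180 and 240 min, with a value below the cut as the event.

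- Usual-care event rate = Φ((cut − 180)/95): 10%, 26%, 50%, 74%.
- Light event rate = Φ((cut − 120)/95): 26%, 50%, 74%, 90%.
- Odds ratios: 3.1, 2.8, 2.8, 3.1.

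Under this model the event rate depends heavily on the cut and the underlying odds ratio hardly does. With 5 per arm, however, an estimated odds ratio would be very uncertain. If 4/5 improved on light and 2/5 on usual care (assumed counts), OR = (4/1)/(2/3) = 6.0 and SE(ln OR) = √(1/4 + 1/1 + 1/2 + 1/3) = 1.44. The 95% CI is exp(ln 6 ± 1.96 × 1.44), about 0.35 to 102.

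**3. What would a linear model deliver?** Inputs: the Aim 1 planning SDs, 95 min and 180 ng (taken as ng/h, the unit in which amplitude is recorded), 5 analysable patients per arm, one value each, no covariates. Half-width = t × SD × √(1/n₁ + 1/n₂).

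| Comparison | t (df) | Misalignment | Amplitude |
|---|---|---|---|
| 5 v 5, variance pooled over three arms | 2.179 (12) | 95 × √(2/5) × 2.179 = 131 min | 180 × √(2/5) × 2.179 = 248 ng/h |
| 5 v 5, two arms only | 2.306 (8) | 139 min | 263 ng/h |
| 10 v 5, any light v usual care, three-arm variance | 2.179 (12) | 95 × √(3/10) × 2.179 = 113 min | 215 ng/h |

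Urine collection stops at MICU discharge and median ICU stay is 3 days, so fewer patients may be analysable. With 4 per arm (9 df) the first row becomes 152 min and 288 ng/h. With 3 per arm (6 df) it becomes 190 min and 360 ng/h. Each covariate costs a further degree of freedom.

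**The case against.** The best defence is that this is a drafting matter in a pilot. The paragraph inherits its outcomes from Aim 1, the word may be a slip for linear, and the raw values will be on file. No model extracts much from 5 patients per arm: a half-width of 131 min sits beside a planning mean of 180 min. A pre-stated responder definition would also make the sentence workable. All of that is fair. It limits the consequence but does not remove the conflict between the named model and the defined outcomes, and if the word is a slip it is easily corrected.

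A reader might infer more than the documents support:

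- **That no effect size can be produced.** It can. Arm means and SDs are computable from the recorded data; the plan just does not ask for them.
- **That the split must be chosen after the data are seen.** The documents only leave it unstated. It could still be fixed before analysis.
- **That no pre-treatment value exists.** The schedule gives one pre-light night.
- **That the logistic fit would usually break down because an arm is all-or-none.** How often this happens depends on response rates, within-patient correlation and covariates that the plan does not give, and on exact 5/5/5 arms. Unrestricted simple randomisation of 15 patients gives that split with probability 15!/(5!)³/3¹⁵, about 5%. Penalised likelihood would also give finite estimates. Breakdown is a separate small-sample risk and is not needed for this point.
- **That the next trial's endpoint will be in minutes or ng/h.** The documents describe later work aimed at delirium and do not fix its endpoint.

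**Conclusion.** The point holds as a specification error. The model named for Aim 3 conflicts with the plan's own definition of the outcomes, and the split and reference value that it would need are not stated. The conflict follows from the text alone and needs no numerical assumption. It should be corrected, but it concerns the written analysis and not the data to be collected, and it leaves the feasibility conclusions untouched.

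A linear analysis gives an estimate in usable units, with a half-width of about 131 to 139 min and 248 to 263 ng/h for a pairwise comparison. Those figures rest on the Aim 1 SDs applying to the pilot, on 5 analysable patients per arm, and on reading the amplitude SD as ng/h. The gain is interpretability and a pre-stated analysis, not precision.

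**What to change.** In the Aim 3 Analytical Approach, replace multivariable logistic regression with a linear model for each outcome in its own units (minutes; ng per hour), with randomised arm as the factor and at most one or two covariates named in advance. State before analysis:

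- whether the outcome is the on-treatment level or the change from the pre-light night;
- the arm coding (three levels, or any light v usual care);
- how a patient with no detectable rhythm is handled for misalignment, since such a patient has no clear peak to time.

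Prefer one summary value per patient. If repeated values are kept, use a small-sample correction and not the default robust standard errors from Aim 1's estimating equations. In a simulation with 5 per arm, three values each and an assumed autoregressive correlation of 0.5, nominal 95% intervals covered only about 89%.

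Report arm means, SDs, mean differences with 95% CIs and numbers analysed as planning estimates, and show individual values. A responder outcome, if also wanted, needs its split and reference value defined in advance.

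The cost is a few sentences, with no new data or visits. The downsides are that chance imbalance on the remaining Aim 1 covariates stays unadjusted, and that one extreme patient can move an arm mean, which is why individual values should be shown.

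### For Aim 3 the plan names only a logistic model, on an undefined yes/no event, for two outcomes it records as continuous, so the between-arm mean difference that would inform the large trial is not planned

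*Combined protocol and SAP*

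**What the plan says.** All references are to the combined protocol and SAP.

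- **Aim 3 Analytical Approach, Effect Size.** Circadian abnormalities are to be assessed in the same way as in Aim 1. The only model then named is: "Using multivariable logistic regression, we will test for associations between bright light exposure and decreases in circadian misalignment and increases in circadian amplitude". The next sentence gives its use: "The estimated association will inform the effect size in the design of future interventional studies". The Aim 3 Rationale likewise gives effect size for the later large trial as a purpose of the pilot.
- **Aim 1 Analytical Approach.** Both outcomes are measured on continuous scales. For misalignment: "The degree of misalignment versus normal will be recorded in minutes". Amplitude "will be recorded in nanograms (ng) per hour".
- **Aim 1 Testing for Associations.** The scale is given as the reason for the model: "Because both measures of circadian abnormality (misalignment and decreased amplitude) are continuous and normally distributed, multivariable linear regression models will test for associations".
- **Aim 1 Power Calculations.** The planning values are a mean and SD for each outcome. On misalignment the text reads: "For minutes of misalignment, we further assume a mean of 180 minutes with a standard deviation of 95". The matching amplitude values are 450 ng (mean) and 180 ng (SD).
- **Aim 3 Research Design.** There are three arms of 5: usual care, 4 hours of light and 8 hours of light.

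**The concern.** A logistic model needs a categorical outcome, and the plan does not say what it is. A decrease in misalignment could mean a fall from the patient's own baseline, crossing a normal limit, or simply a lower value than under usual care, which is how Hypothesis 3.2 can be read. No cut-point, baseline or time window is given, no covariates are listed for a model described as multivariable, and no reason is given for leaving the linear model used in Aim 1.

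What is at stake is the usefulness of the pilot's effect-size result. A later trial with misalignment or amplitude as a continuous outcome is designed from a mean difference and an SD. The Aim 3 text commits to neither, and leaves both the event and the reported quantity open until after the data are seen.

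**Working it through.** The plan states no power, precision or sample-size figure for Aim 3, so there is none to reproduce. The checks below show what the named model would deliver and what a continuous comparison would deliver.

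**Inputs from the plan.** Arms of 5, 5 and 5; misalignment mean 180 and SD 95 minutes; amplitude SD 180 ng. **Assumptions, not in the plan.** A true benefit of 60 minutes; event rates of 50-70% with light and 30-50% with usual care; within-patient correlation r of 0.2 to 0.8; one outcome per patient; arms of exactly 5, which simple randomisation does not guarantee.

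**1. The odds ratio depends on the event.** Take usual care as N(180, 95) and light as N(120, 95).

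For misalignment below a cut-point c, P = Φ((c − mean)/95):

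| Cut-point (min) | Light | Usual care | Odds ratio |
|---|---|---|---|
| 60 | 0.264 | 0.103 | 3.11 |
| 120 | 0.500 | 0.264 | 2.79 |
| 180 | 0.736 | 0.500 | 2.79 |
| 240 | 0.897 | 0.736 | 3.11 |

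For any decrease from baseline, the SD of change is 95 × √(2(1 − r)). The odds of Φ(60/SD) are compared with a 50% chance under usual care:

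| r | SD of change | Light | Odds ratio |
|---|---|---|---|
| 0.2 | 120.2 | 0.691 | 2.24 |
| 0.5 | 95.0 | 0.736 | 2.79 |
| 0.8 | 60.1 | 0.841 | 5.29 |

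The same 60 minutes therefore appears as anything from 2.2 to 5.3. The normal model follows the plan's description of the outcomes. It puts about 10% of the light arm below zero, so for unsigned minutes these values are illustrative.

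**2. Chance of no finite odds ratio, no covariates (exact).** The estimate is infinite or undefined when an arm has no events or only events. For n patients at rate p this has probability s = pⁿ + (1 − p)ⁿ. The chance that at least one arm is affected is 1 − Π(1 − s).

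| Light / usual care | Light pooled, 10 v 5 | Three arms of 5 |
|---|---|---|
| 50% / 50% | 6.4% | 17.6% |
| 70% / 50% | 8.9% | 35.5% |
| 50% / 30% | 17.2% | 27.1% |
| 70% / 30% | 19.4% | 42.9% |

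Worked case, 70%/30% pooled: 0.7¹⁰ + 0.3¹⁰ = 0.0283 and 0.3⁵ + 0.7⁵ = 0.1705, so 1 − 0.9717 × 0.8295 = 0.194. In simulation with two unrelated covariates, over the first, second and fourth rate pairs, the figures are 8-23% pooled and 21-46% with three arms.

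**3. Information kept after splitting a normal outcome.** φ(z)²/(p(1 − p)) is 0.637 at a median split and 0.490 at a 20/80 split. Of 15 patients, that leaves the weight of 15 × 0.637 = 9.6 or 15 × 0.490 = 7.3.

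**4. Precision of the continuous comparison.** The 95% half-width is t × SD × √(1/n₁ + 1/n₂).

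- 5 v 5, SD pooled over three arms (12 df, t = 2.179): 2.179 × 95 × √0.4 = 131 min; 2.179 × 180 × √0.4 = 248 ng.
- 10 v 5 (13 df, t = 2.160): 2.160 × 95 × √0.3 = 112 min; 2.160 × 180 × √0.3 = 213 ng.

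**5. The SD.** The 95% interval for an SD of 95 is 95 × √(df/χ²): 68 to 157 minutes on 12 df from the pilot, against 83 to 110 on 99 df from 100 patients.

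**The case against.** The strongest reply is that the practical loss is small. Aim 3 is a feasibility pilot judged on 70% thresholds, the minutes and ng per hour are collected whatever model is fitted, and intervals of 112 to 131 minutes either side cannot size a trial around a 60-minute effect. All of that stands, and it limits the weight of the point. It does not justify planning an estimate on an unnamed event when the natural summary costs nothing.

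One could also read the reference to Aim 1 as carrying over its linear model, or take logistic as a slip for linear. The first reading is hard to sustain: that sentence concerns how the abnormalities are assessed, and the next one names the model. If it is a slip, the text needs the same correction.

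If Aim 1's repeated-measures approach were carried over, with several daily cycles per patient, the percentages in step 2 would not apply directly. That is a fair limit on them.

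Four stronger readings are tempting, and the documents do not support them:

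- *The model would almost never give a finite estimate.* With Aim 1's adjustment set ("Models will be adjusted for age, gender, severity of illness, sepsis, risk of OSA, ICU care events per hour, and room temperature variables", counted as nine terms), simulation gives 97-99% with no finite value for pooled light arms and over 99% for three arms. But the Aim 3 text does not say that this set applies. A linear model carrying it would also be nearly useless: 15 − 1 − 9 − 1 = 4 residual df with light pooled, or 3 with two light terms.
- *The large trial would have no SD.* Aim 1 measures the same outcomes in 100 patients under the same eligibility criteria, and step 5 shows that this is the better source.
- *An odds ratio cannot be turned back into minutes.* For a cut-point event it roughly can: ln(OR) × √3/π × 95 gives 54 minutes at 2.79 and 59 at 3.11, against the assumed 60. That needs an SD, not the cut-point. The larger ambiguity lies with change from baseline.
- *The effect-size data are lost.* They are not; only the planned summary is at issue.

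**Conclusion.** The point holds as a mismatch between model and outcome, with the event left undefined. It is established from the text that logistic regression is the only Aim 3 effect-size model named, that no event, reference or covariates are given, and that Aim 1 treats the same outcomes as continuous. The missing item is the between-arm mean difference with its interval.

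The sizes rest on the assumptions listed above. The event definition moves the odds ratio between 2.2 and 5.3 for one fixed benefit. There is no finite value in 6-19% of trials with the light arms pooled and 18-43% with three arms. At most 64% of the information survives the split.

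The consequence is modest, because the raw values are retained and any estimate from 15 patients is descriptive. The change is still worth making before analysis, because it fixes what will be reported and puts it on the scale that design needs.

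**What to change.** In Aim 3 Analytical Approach, Effect Size, replace the logistic sentence with:

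> Misalignment (minutes) and amplitude (ng per hour) will be summarised by randomised arm as means and SDs, with unadjusted mean differences and 95% confidence intervals for each light arm v usual care and for both light arms pooled v usual care. The aMT6s used will be that collected from the start of the first light session (09:00 on study day 2), over the same clock window in every arm. Patients without a usable window or a fitted rhythm will be counted by arm. Results are descriptive.

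If a logistic model is kept as a supplement, state its event and reference, and use at most one or two covariates.

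The cost is a change of wording and one table from samples already planned, with no new data, staff or procedures. Urine collection stops at 72 hours or MICU discharge, so some patients may lack a usable window; the counts make that visible. The estimates remain imprecise, so they can inform the large trial but cannot by themselves fix its size. Its SD is better taken from, or checked against, the Aim 1 cohort.
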